5.7.4.1.5 Pregnancy

A serum pregnancy test will be performed for female subjects at the time points presented in the Schedules of Events (Table 9-1). If a subject becomes pregnant while on the study, this should be reported immediately to the investigator, the subject will be withdrawn from the study and the medical monitor and the subject will be instructed to follow-up

with his or her personal physician. All pregnancies are to be reported as an AE and followed for outcome.

5.7.4.2 Clinical Laboratory Tests

Clinical laboratory and diagnostic screening tests will be performed at the time points presented in the Schedules of Events (Table 9-1) and will be collected in accordance with acceptable laboratory procedures. Clinical laboratory testing will be performed by the clinical study contractor. The clinical laboratory tests that will be performed are presented in Table 5-2. Unused clinical laboratory test samples will not be stored for future use.

Table 5-2: Clinical Laboratory Tests and Diagnostic Screening Tests

Hematology	Serum Chemistry	Urinalysis	Lipid Panel
Hematocrit Hemoglobin Platelet count Red blood cell count White blood cell count (with automated differential)	Alanine aminotransferase Albumin Alkaline phosphatase Aspartate aminotransferase Bicarbonate Bilirubin (total, direct, and indirect) Blood urea nitrogen Calcium Chloride Creatinine (including calculated creatinine clearance) Glucose Lactate dehydrogenase Magnesium Phosphorus Potassium Sodium Total protein Uric acid	Appearance Bilirubin Blood Color Glucose Ketones Leukocyte esterase Microscopic examination: red blood cells, white blood cells, epithelial cells, bacteria, crystals, and casts (if present) Nitrite pH Protein Specific gravity Urobilinogen	Total cholesterol High-density lipoprotein cholesterol (HDL-C) Low-density lipoprotein cholesterol (LDL-C) Triglycerides
Diagnostic Screening	Tests:		
Serum	Urine		Other
Serology (human immunodeficiency virus Ag/Ab Combo 1/2, hepatitis C virus antibody, and hepatitis B surface antigen) Female Subjects Only Human chorionic gonadotropin (for pregnancy)	Drug screen including: ampl benzodiazepines, cannabinoi opiates, phencyclidine, propo	ids, cocaine, alcohol,	SARS-CoV2 molecular test

Clinical laboratory results will be reviewed by the investigator or designee together with data in the eCRF. Any values outside the reference range will be evaluated for clinical significance. If a value is determined to be clinically significant, the subject will be instructed to follow-up with his or her personal physician. The investigator or designee may repeat the clinical laboratory tests if deemed appropriate. The investigator will maintain a copy of the laboratory accreditation and the reference ranges for the laboratory used.

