5.7.2 Pharmacodynamic Assessments

5.7.2.1 Pharmacodynamic Sample Collection

5.7.2.1.1 Primary and Secondary PD Biomarker

Blood samples (5 mL) for primary pharmacodynamic biomarker (peripheral blood LDL-C) and secondary pharmacodynamic biomarker (peripheral blood ApoB) assessment will be collected at the following time points:

- Day -1 (check-in)
- Day 1: 0 (Pre-dose), 24 h
- Day 2, 3, 4, 5, 7, 10, 14, 21, 28, 35, 42, 56, 70, 84

All blood samples for primary and secondary pharmacodynamic biomarker assessments will be collected in the fasted state.

Blood samples will be collected by direct venipuncture or by inserting an IV catheter into the subject's forearm region. Each blood sample will be labeled with subject number, study number, study day, time point, event, and a barcode that matches that belonging to the subject.

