5.8.6 Blinding

The pharmacist (and designated staff member responsible for confirmation of study drug dose) will be unblinded to subject treatment assignment; however, the pharmacist will not perform any study procedures other than study drug preparation and dispensing.

Subjects and staff will be blinded to treatment assignment during confinement. The blind will be maintained through a randomization schedule held by the dispensing pharmacist. Subjects and staff will be informed of a subject's end of study day when discharged from confinement. Subjects and staff will not be informed of the specific treatment arm

assignment. The clinical research nurse will administer the subcutaneous study drug in unit dose containers that are not transparent.

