Drug Administration			×							\vdash		\vdash							H	\vdash	_	\vdash				
PK Concentration/PCSK9 Serum sample			×	×	×	×	×	×	×	×	×	×	×	×	×	×	×	×	×	×	×	×	×	×	×	×
Urine Sample Collection (PD)		×	×									×				-	^	×			×					×
Complete Lipid Profile and ApoB	×	×	×									×	×	×	×	×	×	×	×	X	×	×	×	×	×	×
Genomics (buffy coat)			×																	***************************************						
Proteomics & Small RNA Transcriptomics (plasma)		×	×	×	×	×	×	×	×	×	×	×	×	×	×	×	×	×	×	×	×	×	×	×	×	×
Concomitant Medications	×	×	×								_	×	×	×	×	×	×	×	×	×	×	×	×	×	×	×
A demand of the same	,	>	;	Γ				H	H	-	-	-	-	-	-	-	3	2	,	,	-	;	-	-	2	3

¹ Clinically notable results are repeated 2 Serum test

10.Reference List

- 1. Repatha Package Insert dated 08/27/2015. Found at https://www.accessdata.fda.gov/drugsatfda_docs/label/2015/125522s000lbl.pdf
- Praluent Package Insert dated 07/24/2015. Found at https://www.accessdata.fda.gov/drugsatfda_docs/label/2015/125559Orig1s000lbl edt.pdf

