3.1. Study Design

This is a randomized, double-blind, placebo-controlled, single-dose, parallel arm, pilot study. Healthy subjects will be randomized to one of four dose groups (low, intermediate low, intermediate high, and high) for each drug (evolocumab or alirocumab) or placebo (See Table 1). The study will be conducted at one center in the United States (Spaulding Clinical Research unit in West Bend, Wisconsin).

All subjects will be sampled daily for the first week. Subjects in groups A, B, E, and F will follow the schedule of events through day 42. Subjects in groups C and G will follow the schedule of events through day 56. Subjects in groups D, H, and I will follow the schedule of events through day 84. Each treatment group should include equal representation of male and female subjects.

Table 1: Study Treatment Groups

Subjects (n)	Treatment Group	Drug
8	A	Evolocumab low (21 mg) subcutaneously (SC)
8	B	Evolocumab intermediate low (35 mg) SC
8	C	Evolocumab intermediate high (70 mg) SC
8	D	Evolocumab high (140 mg) SC
8	E	Alirocumab low (15 mg) SC
8	F	Alirocumab intermediate low (25 mg) SC
8	G	Alirocumab intermediate high (50 mg) SC
8	H	Alirocumab high (100 mg) SC
8	I	Placebo SC

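### The documents conflict on whether the investigator sees post-dose LDL-C; read as written, the protocol shows the drugs' direct effect to the person who rates AE relatedness under a stated blind.

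*Protocol*

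**What the plan says.** Protocol 5.7.4.2 defines the clinical laboratory tests by a table: "The clinical laboratory tests that will be performed are presented in Table 5-2". That table has a Lipid Panel column whose last entries are "Low-density lipoprotein cholesterol (LDL-C) Triglycerides". Timing is set by the schedule: "Clinical laboratory and diagnostic screening tests will be performed at the time points presented in the Schedules of Events (Table 9-1"). The only lipid row there is "Complete Lipid Profile and ApoB", marked at 24 h, through the first week and at the outpatient visits. Section 5.7.2.1.1 gives the LDL-C draws as pre-dose and 24 h, then "Day 2, 3, 4, 5, 7, 10, 14, 21, 28, 35, 42, 56, 70, 84".

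Section 5.7.4.2 then says who reads the results: "Clinical laboratory results will be reviewed by the investigator or designee together with data in the eCRF". Out-of-range values are assessed for clinical significance and tests may be repeated. No exception is made for lipids.

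On blinding, Protocol 5.8.6 says "Subjects and staff will be blinded to treatment assignment during confinement", and SAP 3.1 says "This is a randomized, double-blind, placebo-controlled, single-dose, parallel arm, pilot study". The means described are a randomization schedule held by the pharmacist, an unblinded pharmacist and dose verifier, and opaque containers. At discharge from confinement, staff and subjects learn the end-of-study day but not the arm.

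**The concern.** Both drugs act by lowering LDL-C, so a subject's post-dose LDL-C carries information on whether active drug was given. The investigator who would read it also rates the relatedness of each AE (5.7.4.1.4), may withdraw a subject on clinical judgement (5.5) and may order repeat tests (5.7.4.2).

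These judgements reach the reported results. TEAEs are summarised by relationship to treatment (Protocol 5.9.8.1, SAP 7.7.1). An abnormal laboratory finding can itself be an AE (5.7.4.1.1). SAP Section 5 drops early-termination subjects from the PK and PD parameter summaries; in an arm of 8, one such subject is 1/8 = 12.5% of the arm unless replaced. A blind that covers the injection but not the lipid report protects these judgements less than the SAP's double-blind label implies.

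**Working it through.** **1. Is post-dose LDL-C within the investigator's review?**

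| Points to yes | Points to no |
|---|---|
| Table 5-2 puts the lipid panel among the clinical laboratory tests | Synopsis (Safety Assessments), 5.1.2, 5.6.2, 5.6.3.1, 5.6.4, 5.7.4, 5.9.8.2 and SAP 7.7.2 name only hematology, chemistry and urinalysis |
| Exclusion criterion 16 also counts the lipid panel as a clinical laboratory result, though at Screening | 5.6.2 to 5.6.4 list LDL-C/ApoB collection apart from the clinical laboratory tests |
| The Synopsis says LDL-C and ApoB are determined within a lipid panel | 5.7.2 treats LDL-C as a pharmacodynamic assessment; Table 5-2 omits ApoB |
| 5.7.4.2 has no lipid exception; no section withholds lipid results | Table 9-1 separates chemistry and hematology from the lipid row |

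The right-hand column suggests that post-dose lipids may not have been meant for safety review. None of it says they are withheld.

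**2. Does access overlap the blind?** Confinement is the first week (5.1). LDL-C draws at 24 h (Day 2) and on Days 3, 4, 5 and 7 fall in or at the end of that week. The overlap is documented.

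**3. What does the end-of-study day already disclose?** From Table 5-1 and Section 5.1:

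- Day 42 (A, B, E, F): 4 × 8 = 32 subjects, placebo 0/32.
- Day 56 (C, G): 2 × 8 = 16 subjects, placebo 0/16.
- Day 84 (D, H, I): 3 × 8 = 24 subjects, placebo 8/24 = 33.3%.

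At discharge from confinement, 32 + 16 = 48 of 72 subjects are already identifiable as active. After that, LDL-C adds active/placebo information only for the other 24.

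**4. How informative could one value be?** There is no plan figure to reproduce: the documents give no LDL-C effect size, time course or within-subject CV, and SAP 3.2 reports no formal sample size calculation. As an illustration, assume a within-subject CV of 9% (range 7% to 12%) and one baseline compared with one post-dose value.

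- Separation: d = fall/(CV × √2). For a 30% fall, d = 0.30/(0.09 × 1.414) = 2.357.
- Accuracy at equal odds: Φ(d/2) = Φ(1.179) = 88.1%.
- Best-rule accuracy when a share p is active, with L = ln[p/(1−p)]: p·Φ(d/2 + L/d) + (1−p)·Φ(d/2 − L/d).
- All 72 subjects: p = 64/72, L = ln 8 = 2.079. Calling everyone active is right in 88.9%.
- Day 84 groups: p = 16/24, L = ln 2 = 0.693. Calling everyone active is right in 66.7%.

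| Assumed fall | Equal odds | All 72 (base 88.9%) | Day 84 groups (base 66.7%) |
|---|---|---|---|
| 20% | 78.4% (72.2–84.4) | 90.6% (89.4–92.5) | 80.5% (75.4–85.7) |
| 30% | 88.1% (81.2–93.5) | 94.0% (91.4–96.5) | 89.0% (82.9–94.0) |
| 50% | 97.5% (93.0–99.4) | 98.6% (96.2–99.7) | 97.7% (93.5–99.5) |

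Ranges run from CV 12% to CV 7%. At CV 9% the gain over knowing nothing is 1.7, 5.1 and 9.7 percentage points across all 72 subjects, and about 14, 22 and 31 points in the Day 84 groups.

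A check that does not depend on allocation is the share of active subjects whose single value falls below the one-sided 95% placebo bound. On the log scale, SD = √[2·ln(1 + CV²)]. For CV 10%, SD = 0.1411; a 30% fall gives Φ(0.3567/0.1411 − 1.645) = Φ(0.883) = 81%. Across CVs of 5%, 10% and 15%, a 10% fall gives 44%, 18% and 13%, and a 30% fall gives 100%, 81% and 52%. Large falls reveal treatment; small ones mostly do not.

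**The case against.** The strongest reply is that no sentence sends post-dose LDL-C to the investigator. That reading joins Table 5-2, the Table 9-1 lipid row and a general review sentence, while at least eight places describe clinical laboratory results without lipids. The lipid panel in Table 5-2 also has an evident screening use (inclusion criterion 3, exclusion criterion 16). This stands to the extent that the fault is a conflict and an omission, not an explicit instruction to show the values. It does not remove the point, because nothing restricts access.

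A second reply is that the blind is limited by design: the end-of-study day identifies 48 of 72 subjects as active. That also stands, and it confines the later effect to the Day 84 groups. It does not cover confinement, when the end-of-study day has not yet been disclosed.

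A third is that this is a descriptive pilot with an assay endpoint and no planned inferential safety comparison. This is correct, and it limits the consequences to investigator judgement.

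A reader might go further in three ways that the documents do not support:

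- That LDL-C unblinds subjects from the first week. Access then is documented, but no time course is given, so how much an early value reveals is an assumption.
- That the equal-odds figures of about 78%, 88% and 98% measure the unblinding. They ignore the 64:8 allocation, under which calling everyone active is right in 88.9%.
- That the primary endpoint is biased or that the exact arm is revealed. LDL-C is measured objectively, and its fall can point to active versus placebo but cannot by itself tell the two drugs apart or fix the dose.

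**Conclusion.** The point holds as a conflict between sections and a gap in the blinding plan, and it should be corrected. As written, the investigator can see post-dose LDL-C during a confinement period that is declared blinded, and later in the 24 subjects of groups D, H and I, whose end-of-study day does not separate placebo from active. What is exposed is AE relatedness, withdrawal and repeat testing.

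The size cannot be fixed from the documents. It rests on an assumed CV, an assumed fall and a single post-dose value. On those assumptions, the gain in correct guesses is small across all 72 subjects and larger in the Day 84 groups.

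**What to change.** In Protocol 5.7.4.2 and 5.8.6, state that post-dose results for the whole lipid panel and ApoB are withheld from blinded site staff, subjects and the blinded sponsor team until database lock, with screening and check-in values still released for eligibility. Reconcile Table 5-2 with Protocol 5.7.4 and 5.9.8.2 and SAP 7.7.2, so that one definition of clinical laboratory results applies throughout. Any safety handling of lipid values is for the sponsor to decide and describe.

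The cost is protocol wording and a laboratory reporting setting; sampling and analysis do not change. The small downside is that the investigator does not see routine lipid values during follow-up.

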5.7.4.3 Vital Sign Measurements

Vital signs (blood pressure, heart rate, respiratory rate, and oral body temperature) will be measured using an automated device at the time points presented in the Schedules of Events (Table 9-1). The subject should be in a supine position, if possible, for a minimum of 5 minutes before vital signs are measured.

5.7.4.4 Safety 12-lead Electrocardiograms

12-lead ECGs will be obtained with the subjects in the supine position for a minimum of 5 minutes before recording. ECGs will be overread by a physician. If an abnormality is observed, the subject will be instructed to follow-up with his or her personal physician.

5.7.4.5 Physical Examinations

A complete physical examination will be performed at the time points presented in the Schedules of Events (Table 9-1).

The complete physical examination will include, but not be limited to, assessments of the head, eyes, ears, nose, throat, skin, thyroid, nervous system, respiratory system, cardiovascular system, abdomen (liver and spleen), lymph nodes, and extremities. Height, weight (without shoes and wearing the lightest possible clothing), and calculation of body mass index will be performed at Screening only.

If a clinically significant abnormality is observed upon physical examination, the subject will be instructed to follow-up with his or her personal physician.

5.7.5 Demographics and Medical History

Demographic data (date of birth, gender, race, and ethnicity) will be collected at Screening.

Each subject will provide a complete medical history at Screening that will be reviewed at Check-in. Specific information relating to any prior or existing medical conditions/surgical procedures will be recorded in the subject's eCRF.

5.8. Study Treatments

For each of the study drugs, doses were selected based on the doses studied in prior PK and PD studies.

5.8.1 Treatments Administered

On Day 1, subjects will receive 1 of the following 9 treatments according to the randomization schedule:

- Treatment Group A: Evolocumab 21 mg SC
- Treatment Group B: Evolocumab 35 mg SC
- Treatment Group C: Evolocumab 70 mg SC
- Treatment Group D: Evolocumab 140 mg SC
- Treatment Group E: Alirocumab 15 mg SC
- Treatment Group F: Alirocumab 25 mg SC
- Treatment Group G: Alirocumab 50 mg SC
- Treatment Group H: Alirocumab 100 mg SC
- Treatment Group I: Placebo

Study drugs will be administered by a clinical research nurse on the study clinic floor at the subject's bedside. The pharmacist and investigator will be available if needed during study drug administration.

5.8.2 Dose Selection

5.8.2.1 Alirocumab

The doses selected for alirocumab are 15mg, 25mg, 50mg, and 100mg single dose SC injection. Alirocumab is eliminated through a target-specific mechanism at low doses and a nonspecific IgG elimination at high doses. The selected dose range will cover the target-specific elimination pathway and thus allow adequate determination of the sensitive dose range for PD similarity comparison based on the dose/area-under-the effect curve (AUEC) relationship of LDL-C lowering effect. In addition, Emax (nadir) will be determined for all doses. These doses have been safely administered to healthy subjects.

5.8.2.2 Evolocumab

The doses selected for Evolocumab are 21mg, 35mg, 70mg, and 140mg single dose SC injection. Evolocumab is eliminated through a target-specific mechanism at low doses and a nonspecific IgG elimination at high doses. The selected dose range will cover the target-specific elimination pathway and thus allow adequate determination of the

sensitive dose range for PD similarity comparison based on the dose/area-under-the effect curve (AUEC) relationship of LDL-C lowering effect. In addition, Emax (nadir) will be determined for all doses. These doses have been safely administered to healthy subjects.

5.8.3 Method of Assigning Subjects to Treatment Sequence

5.8.3.1 Randomization Process

The project biostatistician will create the specifications that will be used to generate the randomization schedule. The specifications will be based on the protocol requirements and appropriate statistical programming with consideration for study design, number of treatments, number of subjects planned for enrollment, stratification, and blocking.

Based on these specifications, the project biostatistician (or designee) will generate a dummy randomization schedule. The schedule is generated using R.

The project biostatistician (or designee) distributes the 'dummy' randomization schedule to specified personnel for review. Any change (e.g., change in block size, change in stratification levels) that requires an update to the specifications will reset this process. Minor changes (e.g., display formatting) will not require a change to the specifications.

After the approval of the 'dummy' randomization schedule, the project biostatistician generates the final randomization schedule. The output is sent only to designated unblinded recipients at the site, who will maintain a secured digital and printed copy for their use.

Archival of the programs and output is accomplished by the creation of an encrypted, password-protected ZIP file containing the program and output file(s). The ZIP file is copied to a secure storage drive at the sponsor's site.

Randomization will occur after informed consent is obtained, either after completion of check-in procedures on Day -1 or just before dosing on Day 1. Approximately 72 healthy male and female subjects are planned for enrollment. Up to 14 subjects may be qualified as replacements as described in Section 5.5.2. Thus, a maximum of 86 subjects will be exposed to study drugs and procedures during the study. Unique subject numbers will be used in sequential order based on each subject's order of qualification.

Enrolled subjects will be randomly assigned to 1 of 9 different treatment groups.

The treatment groups are presented in Table 5-3.

Table 5-3: Study Treatment Groups

Subjects (n)	Treatment Group	Drug
8	A	Evolocumab low (21 mg)
8	В	Evolocumab intermediate low (35 mg)
8	C	Evolocumab intermediate high (70 mg)
8	D	Evolocumab high (140 mg)
8	Е	Alirocumab low (15 mg)
8	F	Alirocumab intermediate low (25 mg)
8	G	Alirocumab intermediate high (50 mg)
8	Н	Alirocumab high (100 mg)
8	I	Placebo

All randomization information will be secured and housed in a locked storage area, accessible only by the randomization personnel and the assigned pharmacist and his or her verifier.

5.8.4 Identity of Study Drugs

[®]Alirocumab (PRALUENT[®]) is a PCSK9 (Proprotein Convertase Subtilisin Kexin Type 9) inhibitor antibody indicated as adjunct to diet and maximally tolerated statin therapy for the treatment of adults with heterozygous familial hypercholesterolemia or clinical atherosclerotic cardiovascular disease, who require additional lowering of LDL-C. Alirocumab has a molecular weight of 146 kg/mol (146 kDa) and the molecular formula C₆₄₇₂H₉₉₉₆N₁₇₃₆O₂₀₃₂S₄₂. The physical form is available as 75 mg/ml or 150 mg/ml solution in a single-dose pre-filled pen/syringe.

Evolocumab (REPATHA®) is a PCSK9 inhibitor antibody indicated as an adjunct to diet and maximally tolerated statin therapy for treatment of adults with heterozygous familial hypercholesterolemia (HeFH), clinical atherosclerotic cardiovascular disease (CVD), or other LDL-lowing therapies in patients with homozygous familial hypercholesterolemia (HoFH), who require additional lowering of LDL-C. Evolocumab has a molecular weight of 141.8 kg/mol (144 kDa) and the molecular formula C₆₂₄₂H₉₆₄₈N₁₆₆₈O₁₉₉₆S₅₆. The physical form is available as 140 mg/mL solution in a single-dose pre-filled syringe/SureClick® autoinjector.

Placebo of equal volume and comparable pH for the high dose of each drug will be used as placebo control in this study and administered subcutaneously.

5.8.5 Management of Clinical Supplies

5.8.5.1 Study Drug Packaging and Storage

The active study drugs will be obtained from commercial sources. Storage instructions for the active study drugs are as follows:

- Evolocumab (REPATHA®) should be stored in the refrigerator at 2° to 8°C (36° to 46°F) in the original carton to protect from light. Do not freeze. Do not shake. Prior to use, allow evolocumab to warm to room temperature for at least 30 minutes. Do not warm in any other way. Alternatively, for patients and caregivers, evolocumab can be kept at room temperature (up to 25°C (77°F)) in the original carton. However, under these conditions, evolocumab must be used within 30 days.
- Alirocumab (PRALUENT) should be stored in a refrigerator at 36°F to 46°F (2°C to 8°C) in the outer carton in order to protect from light. Do not freeze. Do not expose to extreme heat. Do not shake. Alirocumab should be allowed to warm to room temperature 30 to 40 minutes before use. Do not keep PRALUENT at room temperature for more than 24 hours.
- Placebo should be stored below 25 °C (77 °F). Do not freeze. Vials should be protected from the light until time of use.

